## **1. Background and Rationale**

Anxiety disorders are among the most prevalent psychiatric conditions worldwide, impairing quality of life and daily functioning. Despite effective treatments such as pharmacotherapy and cognitive-behavioral therapy, many patients remain partially symptomatic or experience side effects. Complementary and Integrative Practices (CIP) have gained attention as supportive strategies, and reflexology is one of these practices recognized by the Brazilian Unified Health System (SUS).

Foot reflexology is a non-invasive manual technique that applies pressure to specific reflex points on the feet, believed to correspond to organs and systems in the body. Preliminary studies suggest potential benefits in reducing anxiety and promoting relaxation, but further randomized controlled trials with rigorous methodology are needed.

## **2. Objectives**

Primary Objective:

- To evaluate the effect of foot reflexology on anxiety symptoms, measured by the Beck Anxiety Inventory (BAI).

Secondary Objectives:

- To assess changes in psychological well-being and relaxation using the Tension-Anxiety subscale of the Profile of Mood States (POMS, reduced version).
- To record and analyze adverse effects related to the interventions.

## **3. Study Design**

This is a randomized, parallel, controlled, double-blind clinical trial with two arms:

1. Foot reflexology intervention.
2. Sham reflexology (control group).

The study will last approximately 5 weeks, with 10 intervention sessions per participant.

## **4. Eligibility Criteria**

Inclusion Criteria:

- Adults aged 18–80 years.
- Clinical diagnosis of anxiety disorder (confirmed by physician or psychologist).
- BAI score  $\geq 11$  (mild anxiety or higher).
- Ability to attend all intervention sessions and assessments.

Exclusion Criteria:

- Current psychiatric or psychological treatment with medication adjustments in the last 30 days.
- Use of other complementary therapies for anxiety during the study period.
- History of severe psychiatric disorders (psychosis, bipolar disorder).
- Foot injuries, ulcers, or contraindications to manual therapy.
- Pregnancy.

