## **6. Outcome Measures**

Primary Outcome:

- Reduction in anxiety symptoms assessed by Beck Anxiety Inventory (BAI).
- Score range: 0 to 63.
- Higher scores indicate worse anxiety.

- Time points: baseline, after session 5, after session 10.

Secondary Outcomes:

- Tension-Anxiety Subscale of the Profile of Mood States (POMS – reduced version).
- Score range: 0 to 36.
- Higher scores indicate worse tension-anxiety.
- Time points: after each of the 10 sessions.
- Adverse effects.
- Recorded during and after each session.
- Frequency and intensity analyzed descriptively.

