## **7. Randomization and Blinding**

Participants will be randomized into intervention or sham groups using a computer-generated randomization list ([randomization.com](http://randomization.com)). Allocation will be concealed in sealed opaque envelopes.

Blinding:

- Participants will not be informed of the intervention type (reflexology or sham).
- Therapists will be trained but informed only that they are applying a “foot massage technique,” with no access to study allocation. They will not communicate with each other.
- Outcome assessors and data analysts will remain blinded to group allocation.

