## **9. Statistical Analysis Plan**

Descriptive statistics (mean  $\pm$  SD) will be used for quantitative variables.

- Primary outcome (BAI): Repeated measures ANOVA (Group  $\times$  Time) with post-hoc Bonferroni.

- Secondary outcomes (POMS): Repeated measures ANOVA (Group × Time).
  - Adverse effects: Frequency distribution and Chi-square tests.
- Significance level:  $p < 0.05$ . SPSS (IBM, v.29) will be used.

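### Does the exclusion for other complementary therapies let participants be removed after randomisation and so bias the BAI comparison?

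*Protocol*

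**What the plan says.** Protocol section 4 (Eligibility Criteria) has, under exclusions, "Use of other complementary therapies for anxiety during the study period". The exclusion just above it uses a look-back window: "Current psychiatric or psychological treatment with medication adjustments in the last 30 days". Among the inclusions is another item that looks forward: "Ability to attend all intervention sessions and assessments".

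Section 3 (Study Design) fixes the period: "The study will last approximately 5 weeks, with 10 intervention sessions per participant". Section 6 (Outcome Measures) sets the BAI schedule: "Time points: baseline, after session 5, after session 10". Both follow-up measurements therefore fall inside the window that the exclusion names.

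The primary-analysis line in section 9 (Statistical Analysis Plan), which begins "Primary outcome (BAI): Repeated measures ANOVA (Group", names no analysis set and excludes no one. Sections 5, 7, 8 and 9 contain no rule for participants who start another therapy: no withdrawal, no removal and no end to assessment.

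**The concern.** An entry criterion should be decidable at entry. This one is worded as an event over the whole study, so part of it cannot be known when a participant is randomised. Its neighbours describe a history, a present state or a past window. Two members of staff could apply it differently, each in good faith: one asks about current and planned use at screening, the other treats a week-3 user as having become ineligible.

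Under the second reading, participants would be taken out because of something they did after randomisation. In people with an anxiety disorder, seeking further help is plausibly linked to persisting symptoms, which is what the BAI measures. If reflexology works, more poor responders would leave the sham arm than the reflexology arm, and the contrast would shrink. If BAI assessment also stopped for those participants, no later analysis rule could recover their data.

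**Working it through.** **Text.** Three facts from the Protocol bear on the reading.

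1. The line stands in the list that decides who enters.
2. The attendance item in the same list also looks forward, and it can only be judged at screening. Reading the complementary-therapy line the same way, as current or planned use, is consistent with it.
3. The contrast with the 30-day medication window shows that the two windows differ. It does not show that this line operates after randomisation.

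Bias therefore needs four things together: application after randomisation, removal from assessment or analysis, uptake related to anxiety, and a true treatment effect. The Protocol states none of them.

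**Size if all four held.** The Protocol states no related figure, so there is none to reproduce, and every input below is an assumption. Let the outcome in SD units (higher is worse) be N(0,1) on sham and N(−d,1) on reflexology. Let the propensity to take up another therapy be U = ρY + √(1−ρ²)e, with removal if U > c and c = z(1−p), where p is the share of sham removed. The same rule holds in both arms, which is reasonable while participants do not know their allocation (section 7). Then:

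- estimate = d + ρ[φ(c+ρd)/Φ(c+ρd) − φ(c)/Φ(c)]
- share of reflexology removed = 1 − Φ(c+ρd)

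Worked case, d = 0.5, p = 0.15, ρ = 0.5: c = 1.0364 and c+ρd = 1.2864. The ratios are 0.1744/0.9009 = 0.1936 and 0.2332/0.85 = 0.2743. The estimate is 0.5 + 0.5 × (0.1936 − 0.2743) = 0.4596, a shortfall of 0.0404 (8.1%). Reflexology loses 9.9%.

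**Cost of keeping later users in.** If the other therapy improves the outcome by b SD, retained users dilute the contrast by b × (p − reflexology share). In the worked case the difference in shares is 0.15 − 0.0991 = 0.0509. Dilution is 0.0254 at b = 0.5 and 0.0407 at b = 0.8. It equals the shortfall avoided at b = 0.0404/0.0509 = 0.79.

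All cases at d = 0.5:

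| ρ | Sham removed | Reflexology removed | Estimate | Shortfall | Break-even b |
|---|---|---|---|---|---|
| 0.3 | 5% | 3.6% | 0.4922 | 0.0078 (1.6%) | 0.57 |
| 0.3 | 10% | 7.6% | 0.4880 | 0.0120 (2.4%) | 0.50 |
| 0.3 | 15% | 11.8% | 0.4848 | 0.0152 (3.0%) | 0.47 |
| 0.3 | 20% | 16.1% | 0.4822 | 0.0178 (3.6%) | 0.45 |
| 0.5 | 5% | 2.9% | 0.4798 | 0.0202 (4.0%) | 0.96 |
| 0.5 | 10% | 6.3% | 0.4684 | 0.0316 (6.3%) | 0.85 |
| 0.5 | 15% | 9.9% | 0.4596 | 0.0404 (8.1%) | 0.79 |
| 0.5 | 20% | 13.75% | 0.4525 | 0.0475 (9.5%) | 0.76 |

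At d = 0.3 the estimates run from 0.2952 (1.6% low) to 0.2704 (9.9% low). With d = 0 or ρ = 0 the bracket is zero, so there is no bias.

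**The case for a change.** The best case for a change is that eligibility wording, and whether a participant goes on being assessed, belong to the Protocol and not to the SAP. A literal reader could stop BAI collection, and that loss is permanent. Adding a few words at screening and one case-report item would be cheap, and the benefit claimed is a comparison that stays as randomised, not a larger estimate.

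Much of this stands. The ambiguity is real, nothing elsewhere resolves it, and keeping everyone in the randomised groups is the sound principle. What does not follow is that the plan is wrong. The harmful reading must be supplied by the reader, because no section tells anyone to stop assessment or drop a participant. How later users enter the analysis is an intercurrent-event rule that a SAP commonly settles, and recording their use is a case-report detail.

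Replacing the line with a purely screening-based one also has a cost. It would delete the words about the study period, which are the Protocol's only statement on use of other therapies while the trial runs. The dilution figures assume that uptake would not change as a result.

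**Conclusion.** The wording is loose, but no change to the plan is called for. Read in its place, the line screens out people who use or intend to use another complementary therapy, and a competent team would apply it that way. A sponsor wishing to tidy it could say that it is judged at screening, while keeping its own statement on use during the study. That would be editorial.

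Under the assumptions shown, applying it after randomisation would cost 0.008-0.0475 SD at a true effect of 0.5 SD, always toward no effect and zero when there is none. Retaining users costs a similar amount: at correlation 0.3, dilution exceeds the shortfall once the other therapy's benefit passes 0.45-0.57 SD, and at correlation 0.5 once it passes 0.76-0.96 SD. The figures rest on one uptake rule common to both arms. If uptake rules differed by arm, for example because participants guessed their allocation, the model would not cover it. Nothing in the Protocol allows the real size to be estimated.

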## **5. Interventions**

Foot Reflexology Group:

- Protocol based on classical reflexology charts, applying pressure to reflex points related to stress and anxiety regulation. Each session lasts approximately 15 minutes per foot, totaling 30 minutes.

Sham Reflexology Group:

- Protocol involving superficial sliding movements and joint mobilization of the foot (hindfoot, midfoot, forefoot), without stimulation of reflex points. Movements include flexion, extension, circumduction, and gentle traction of metatarsophalangeal, tarsometatarsal, and ankle joints. Each session lasts 30 minutes.

## **6. Outcome Measures**

Primary Outcome:

- Reduction in anxiety symptoms assessed by Beck Anxiety Inventory (BAI).
- Score range: 0 to 63.
- Higher scores indicate worse anxiety.

- Time points: baseline, after session 5, after session 10.

Secondary Outcomes:

- Tension-Anxiety Subscale of the Profile of Mood States (POMS – reduced version).
- Score range: 0 to 36.
- Higher scores indicate worse tension-anxiety.
- Time points: after each of the 10 sessions.
- Adverse effects.
- Recorded during and after each session.
- Frequency and intensity analyzed descriptively.

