## **8. Data Collection and Management**

Data will be collected at baseline and throughout the intervention sessions. Each participant will be assigned an anonymous code. Data will be stored in password-protected electronic files accessible only to the research team.

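### The primary BAI is scheduled only by sessions received, so a participant who stops before session 10 has no final BAI as the protocol defines it

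*Protocol*

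**What the plan says.** Section 6 of the protocol lists the BAI assessments as "Time points: baseline, after session 5, after session 10". No day, week or window is attached to either post-baseline assessment. The secondary POMS subscale is also counted in sessions ("Time points: after each of the 10 sessions"), so no other scheduled measurement fills the gap for someone who has stopped.

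Section 8 says "Data will be collected at baseline and throughout the intervention sessions". Section 3 gives the only calendar information: "The study will last approximately 5 weeks, with 10 intervention sessions per participant". It does not tie the BAI to a week. Among the entry criteria in section 4 is "Ability to attend all intervention sessions and assessments". The primary analysis in section 9 is "Primary outcome (BAI): Repeated measures ANOVA (Group $\times$ Time) with post-hoc Bonferroni".

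No section schedules a BAI for a participant who stops early.

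**The concern.** Both post-baseline measurements of the primary outcome are triggered by something that happens after randomisation, namely receipt of the fifth and the tenth session. A site that follows the schedule as written has no occasion to ask for a final BAI from someone who leaves after seven sessions, even if that person would gladly complete the questionnaire.

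What is at stake is which participants are compared. The primary objective in section 2 is not limited to people who finish the course. If final scores exist only for those who do, the comparison at the last time point is between two groups selected after randomisation. A statistical analysis plan can choose a model for missing values, but it cannot supply scores that nobody was told to collect. When and from whom the primary outcome is measured is a protocol decision, and this protocol has made it.

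**Working it through.** The protocol states no dropout rate, sample size, SD or target difference, so there is no figure of its own to reproduce. The check is first on the text and then by illustration.

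**1. Who has which BAI, reading sections 6 and 8 together**

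| Participant stops | Session-5 BAI | Session-10 BAI |
|---|---|---|
| after session 4 | none as defined | none as defined |
| after session 7 | yes | none as defined |
| after session 9 | yes | none as defined |
| not at all | yes | yes |

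A conventional repeated measures ANOVA uses only participants with all time points, so the first three rows would drop out of the primary analysis altogether. A likelihood-based model could use the session-5 score in rows two and three, but would still have no observed final score for them.

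**2. How many this could affect** (assumption: a constant chance d of stopping at each session; d is not in the protocol)

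Share without a session-k BAI = 1 − (1 − d)^k.

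| d | without session-5 BAI | without session-10 BAI |
|---|---|---|
| 1% | 4.9% | 9.6% |
| 2% | 9.6% | 18.3% |
| 3% | 14.1% | 26.3% |
| 5% | 22.6% | 40.1% |

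**3. Bias in the final comparison**

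In one arm, let p be the share not reaching session 10, C the mean improvement of completers and N the mean improvement that non-completers would have shown. The mean over all randomised is (1 − p)C + pN, so the completers' mean exceeds it by p(C − N). The between-arm bias is the difference of this quantity between the arms. All inputs below are assumed:

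- 20% against 10% stopping, gap of 5 points in both arms: 0.20 × 5 − 0.10 × 5 = 0.5 points.
- 30% against 10%, gap of 8 points in both: 0.30 × 8 − 0.10 × 8 = 1.6 points.
- 20% in both arms, gap of 8 points in one and 5 in the other: 0.20 × 8 − 0.20 × 5 = 0.6 points. Equal stopping is not enough to remove the bias.
- Equal stopping and equal gaps: 0.

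When stoppers improve less, the bias favours the arm with the larger p(C − N), which could be either arm.

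**4. Timing**

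Ten sessions in about 5 weeks is 35 / 10 = 3.5 days per session, so a participant on schedule reaches sessions 5 and 10 at about week 2.5 and week 5. If two sessions were missed and made up later, the final BAI would come about 2 × 3.5 = 7 days late, or 7 / 35 = 20% of the planned period. The protocol has no rule on make-up sessions, so this too is an assumption.

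**The case against.** The strongest reply is that silence is not prohibition. Section 8 contains no limiting word, section 4 mentions assessments as well as sessions, and a site could still ask a participant who has left for a BAI. That is right, and a reader who infers that the protocol forbids such collection goes beyond the text. What stands is narrower: no time point is defined for it, so any such score would be ad hoc and would belong to no planned level of the analysis.

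A reader might also infer that the reflexology arm will lose more participants because pressure causes soreness. The protocol does not support this. Section 10 assigns local reactions to neither arm, calls them mild, and expects them to resolve within 48–72 hours, which is shorter than the average spacing of 3.5 × 24 = 84 hours. The sham in section 5 also involves joint mobilisation and traction. Differential stopping is possible but not shown.

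A third tempting reading is that late attendance biases the result. If delay is similar in both arms, natural course and regression to the mean act alike in both, and the drift mainly adds noise. Section 3 also supplies a nominal calendar for anyone on schedule.

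Two further points have weight. Missing-data handling may be set out in an analysis plan that is not shown, and a model using session-5 scores could reduce the loss. The attendance criterion should also make stopping less common. Neither yields a final score for someone who stops, and the criterion is a judgement at entry, not a follow-up rule.

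**Conclusion.** The point holds as a defect in the outcome schedule. As the protocol is written, a final BAI is defined only for participants who receive session 10, and any post-baseline BAI only for those who receive session 5. Combined with the repeated measures ANOVA, the final comparison would be one of completers.

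Whether that comparison is biased depends on whether stopping, or the outcome of those who stop, differs by arm. The protocol neither shows nor excludes either. The range of 0.5 to 1.6 BAI points rests wholly on assumed stopping rates and gaps, and the bias is 0 with equal stopping and equal gaps. With no SD or target difference stated, these amounts cannot be set against the effect the trial hopes to find. Timing drift among late attenders is secondary. The change should still be made, because it is cheap beforehand and uncollected scores cannot be recovered afterwards.

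**What to change.** **Section 6.** Give each post-baseline BAI a nominal time from randomisation or from the first session, about week 2.5 and week 5, with a stated window. State that it is sought from every randomised participant whatever number of sessions was received. Because section 3 gives only an approximate length, the sponsor must confirm these nominal times first.

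**Section 8.** Extend data collection to participants who have stopped the sessions, and record for each BAI its date and the number of sessions attended by then.

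The session schedule need not change, and for participants on schedule the BAI falls where it does now.

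**Cost.** A change of wording in two sections, and a self-report questionnaire by phone, post or online for those who have stopped or fallen behind. There are two downsides. Some scores will reflect fewer than 5 or 10 sessions, so the estimate may be somewhat smaller than one for the full course; for late attenders this is a real trade-off, and the attendance record lets it be examined. Remote completion may also differ in mode from completion at a session, and that difference would be tied to stopping, so the mode should be recorded as well.

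### POMS Tension-Anxiety has no measurement before treatment, so change from the untreated state and adjustment for its own baseline are unavailable

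*Protocol*

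**What the plan says.** Protocol section 6 gives each scale its own schedule. For the BAI it is "Time points: baseline, after session 5, after session 10". For POMS Tension-Anxiety it is "Time points: after each of the 10 sessions".

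The objective in section 2 is "To assess changes in psychological well-being and relaxation using the Tension-Anxiety subscale of the Profile of Mood States". Section 9 gives the POMS analysis as "Secondary outcomes (POMS): Repeated measures ANOVA (Group × Time)" and names no covariate.

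Section 8 adds a general sentence, "Data will be collected at baseline and throughout the intervention sessions", without naming an instrument. No section schedules POMS before the first session.

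**The concern.** The first POMS value is taken after session 1, when treatment has begun, so it cannot stand for the untreated state. Three things follow.

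- **Change.** The schedule supports change across sessions 1 to 10. It does not support change from before treatment, which is what a reader would expect an objective about changes to mean.
- **Precision.** The between-arm POMS comparison cannot be adjusted for baseline POMS. Baseline BAI is available, but only as a partial proxy.
- **Interaction test (a lesser point).** With no pre-treatment level, the Group × Time term cannot register a benefit that is present from session 1 and constant thereafter. The group main effect of the same model can.

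This is a matter of data collection, so an analysis plan written later cannot repair it.

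**Working it through.** The protocol states no figure on this point, so there is none to reproduce. The check compares the schedules and then sizes the loss on stated assumptions.

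**Schedules**

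| Scale | Time points (section 6) | Before treatment | After treatment has begun |
|---|---|---|---|
| BAI | 3 | 1 | 2 |
| POMS Tension-Anxiety | 10 | 0 | 10 |

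The general sentence in section 8 is fully satisfied by the BAI baseline and does not override the scale-specific list in section 6.

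**Assumptions** (none is in the protocol except the ten sessions and the 5% level, for which two-sided testing is assumed): n = 30 or 50 per arm; constant benefit 0.5 SD; between-session correlation ρ = 0.6 (0.8 as a variant); correlation r of baseline POMS with later POMS 0.3 to 0.5. For baseline BAI as proxy, a correlation of 0.5 to 0.7 with baseline POMS is assumed. If BAI predicts later POMS only through baseline POMS, r is then 0.5 × 0.3 = 0.15 to 0.7 × 0.5 = 0.35.

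**Group effect averaged over the ten sessions**

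- Variance of a participant's mean, in SD² units: V = (1 + 9ρ)/10. At ρ = 0.6, V = 0.64; at ρ = 0.8, V = 0.82.
- With the covariate: V − r². At ρ = 0.6 this is 0.64 − 0.09 = 0.55 for r = 0.3 and 0.64 − 0.25 = 0.39 for r = 0.5.
- Standard error: √(2V/n). At n = 30 without a baseline this is √(2 × 0.64/30) = 0.207.
- Power from the noncentral t with 2n − 2 degrees of freedom, or 2n − 3 with the covariate. The 95% CI half-width is the t quantile times the standard error, for example 2.00 × 0.207 = 0.41.

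| | No baseline | Baseline BAI as proxy | Baseline POMS |
|---|---|---|---|
| Power, ρ = 0.6, n = 30 | 66% | 68–75% | 73–86% |
| Power, ρ = 0.6, n = 50 | 87% | 88–93% | 92–98% |
| Power, ρ = 0.8, n = 30 | 56% | – | 61–71% |
| Power, ρ = 0.8, n = 50 | 78% | – | 83–91% |
| CI half-width, ρ = 0.6, n = 30 | 0.41 SD | – | 0.38–0.32 SD |
| CI half-width, ρ = 0.6, n = 50 | 0.32 SD | – | 0.29–0.25 SD |
| n per arm for 80% power, ρ = 0.6 | 42 | – | 36–26 |

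Simulation at ρ = 0.6 (6000 trials per setting) agrees. At n = 30 it gives 66–67% unadjusted, and 73.0% and 86.2% adjusted. At n = 50 it gives 87–88%, and 91.4% and 97.8%.

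**What the session 1-to-10 change shows of a 0.5 SD arm difference at session 10**

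- Linear growth from 0.05 to 0.5: 0.5 − 0.05 = 0.45 SD.
- Plateau at session 3 (0.17, 0.33, then 0.5): 0.5 − 0.17 = 0.33 SD.
- Full benefit from session 1: 0.5 − 0.5 = 0.

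**Interaction term under a constant benefit**

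The arm differences at the ten post-session points are all 0.5, so their sum of squares about their mean is 0 and the test rejects at its nominal 5%. With a baseline level (difference 0) added, the sum of squares is 0.5² × 10/11 = 0.227. Simulated rejection is then 39–42% (n = 30) and 59–67% (n = 50), or 34–38% and 55–65% with the Greenhouse-Geisser correction.

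**The case against.** The strongest points on the other side are these.

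- **The objective does not say change from baseline.** Ten repeated measurements with Group × Time do assess change across sessions. This is correct, so the text is not in outright contradiction. The schedule still leaves out the change of most interest, and how much is missed depends on the time course: 0.05 SD under linear growth, all of it if the benefit is immediate.
- **A POMS baseline may be intended.** Section 8 speaks of baseline data in general. That is possible, but section 6 names baseline for the BAI and not for POMS. If one is intended, section 6 still needs the edit.
- **The precision gain needs the covariate as well as the time point.** Section 9 names no covariate for either scale, so adding the measurement under the ANOVA as written would not give the adjusted figures. This stands. The covariate has to be part of the fix, but it cannot be used unless the value is collected.
- **The figures rest on assumptions and can be modest.** At r = 0.3 the gain is 66% to 73% (n = 30) or 87% to 92% (n = 50), and baseline BAI recovers some of it. This also stands.
- **The effect is bounded.** One secondary outcome is concerned, randomization keeps its comparison unbiased, and the group main effect detects a constant benefit. This limits the weight of the point and does not remove it.

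**Conclusion.** The concern holds. As written, POMS Tension-Anxiety has ten post-treatment values and no pre-treatment value. Change from the untreated state cannot be estimated, and the comparison cannot be adjusted for its own baseline.

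On the assumptions above, the missing covariate costs about 7 to 20 percentage points of power at 30 per arm and 5 to 11 at 50 per arm (ρ = 0.6), or 6 to 16 more participants per arm for 80% power (42 − 36 to 42 − 26). These are illustrations, since the protocol gives no sample size, SD, effect or correlation. The gap in the schedule itself does not depend on them.

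The POMS outcome remains interpretable as a randomized comparison of post-session levels, and the primary outcome is unaffected. The point should be fixed because the remedy is cheap and the loss is permanent for each participant treated without the measurement.

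**What to change.** Add one POMS Tension-Anxiety assessment before session 1, at the existing baseline assessment, to the POMS time points in section 6. Name it in section 9 as a covariate in the POMS analysis. If a POMS baseline is already planned, state it in section 6.

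For participants already treated, restate the section 2 objective as post-session levels (and change across sessions, if that is wanted). Rely on the between-group difference, with baseline BAI as a partial covariate. Which POMS effect is the main test can be left to the SAP.

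The cost is one short questionnaire at a visit that already takes place, because section 4 requires a BAI score for inclusion ("mild anxiety or higher") and section 6 a BAI baseline. The text changes are one time point and one covariate. Anyone already treated will lack the value.

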## **10. Risks and Benefits**

Risks: Mild local reactions in the feet, such as redness, sensitivity, discomfort, or muscle soreness, which typically resolve within 48–72 hours. Transient tingling may occur. Serious adverse effects are not expected.

Benefits: Possible reduction in anxiety symptoms, improved relaxation and well-being, and contribution to scientific knowledge about reflexology.

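### No systematic recording of adverse effects is planned between visits or after session 10, although the expected foot reactions typically take 48–72 hours to resolve

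*Protocol*

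**What the plan says.** Protocol section 2 makes safety a secondary objective: "To record and analyze adverse effects related to the interventions". Section 6 names frequency and intensity as the quantities of interest and fixes the timing as "Recorded during and after each session". It does not say how long the period after a session lasts, who asks, or whether participants are asked about the days since their last visit. Section 8 describes the collection period: "Data will be collected at baseline and throughout the intervention sessions". Section 9 plans the analysis: "Adverse effects: Frequency distribution and Chi-square tests".

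Section 10 lists the expected reactions as "Mild local reactions in the feet, such as redness, sensitivity, discomfort, or muscle soreness", "which typically resolve within 48–72 hours". Section 3 gives the schedule: "The study will last approximately 5 weeks, with 10 intervention sessions per participant". The last BAI assessment comes after session 10 ("Time points: baseline, after session 5, after session 10"), and no section describes a later visit or contact.

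**The concern.** The protocol expects reactions that last two to three days, but describes observation only in connection with sessions, which are on average further apart than that. A reaction noticed at the visit will be recorded. One that begins at home, or that is mild at the visit and worsens afterwards, has no planned point at which anyone asks about it. For the first nine sessions the record then depends on the participant mentioning it at the next visit. After the tenth there is no next visit.

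At stake is the completeness of a stated secondary outcome. Intensity is affected as well as frequency, because a record made at the visit cannot show the later course of a reaction that may last 72 hours. Unprompted reporting can also vary between participants and therapists, and that weakens the between-arm test.

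**Working it through.** The protocol states no figure of its own on this point, so there is none to reproduce. The check is timing arithmetic followed by a reading of the sections side by side.

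**Inputs**
- Study length: about 5 weeks (section 3), which is 5 × 7 = 35 days, or 35 × 24 = 840 hours.
- Sessions: 10 per participant (section 3).
- Time to resolution of expected reactions: 48–72 hours (section 10).
- Spacing between sessions: not stated.

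**Average spacing**
- Counting one interval per session: 840 / 10 = 84 hours.
- Counting the 9 gaps between a first session on day 0 and a last on day 35: 840 / 9 = 93.3 hours.
- Compared with the upper end of the resolution time: 84 − 72 = 12 hours, and 93.3 − 72 = 21.3 hours. On either count the average gap is longer than the typical reaction.

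**Sensitivity to the unstated spacing**

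Assume two sessions a week on fixed weekdays. The two gaps then sum to 7 × 24 = 168 hours.

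| Days between the two weekly sessions | Gaps (hours) | Longer gap above 72 hours? |
|---|---|---|
| 1 | 24 / 144 | yes |
| 2 | 48 / 120 | yes |
| 3 or 4 | 72 / 96 | yes |

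Because the two gaps sum to 168 hours, the longer one is always at least 84 hours. In the first two patterns the shorter gap is below 72 hours, so some reactions would still be present at the next visit.

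**Which sessions have a later observation point**
- Sessions 1–9 (9 of 10) are each followed by another session, where a reaction can be reported from memory. No section says that it is asked for.
- Session 10 (1 of 10) is followed by none.

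**How far the recording period after a session reaches**

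Section 6 sets no end to it. Two things favour a visit-bound reading. The same section uses the same word for BAI and POMS, where it marks an assessment point and not a window of several days. Section 8 ties collection to the sessions. Even if section 8 is read as covering the whole period over which sessions run, that period ends with session 10.

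**The case against.** The strongest reply is that the text excludes nothing. Section 6 does not limit recording to the visit, and its wording includes session 10, so the sponsor may intend the following days to count. This stands to the extent that total non-capture cannot be asserted. It does not close the gap, because no section describes how information from those days would be obtained.

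Second, 48–72 hours is a time to resolution. The protocol describes no delayed onset, and a reaction that starts during or just after a session is recorded then, however long it lasts. This stands fully. Sections 6 and 10 do not contradict each other, and the gap concerns only reactions that begin or worsen after the participant has left.

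Third, for sessions 1–9 a resolved reaction can still be reported at the next visit. This also stands: the 84–93 hours show reliance on unprompted recall, not loss. A reader might infer that late reactions to all ten sessions go unrecorded. That would need both the narrowest reading of section 6 and participants who never mention anything at the next visit, and the protocol supports neither as fact.

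Fourth, a reader might infer that under-recording falls mainly on the reflexology arm and flatters it. The protocol does not support this. The sham in section 5 includes joint mobilization and traction, section 10 does not separate risks by arm, and the recording rule is the same for both.

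Finally, the wording of the question may sit in a case report form or manual that is not shown. That is possible for the wording. When safety data are collected, however, is a protocol matter, and an analysis plan cannot supply observations that were never made.

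**Conclusion.** The point holds as a minor design weakness. The protocol ties adverse-effect recording to sessions and plans no systematic ascertainment between visits or after session 10, while expecting reactions that typically resolve in 48–72 hours. With average spacing of about 84–93 hours, reactions that start or worsen after departure are captured for 9 of 10 exposures only if volunteered, and for the remaining 1 of 10 no capture is planned.

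This rests on two assumptions: that sessions are spread over roughly the full 5 weeks, and that recording after a session means at the visit, as the BAI and POMS usage and section 8 suggest. The number of affected reactions cannot be estimated because no event rate is given, and the direction of any effect on the comparison of arms is not established. The primary outcome is untouched.

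**What to change.** In section 6, state the recording window and add one standard question at the start of sessions 2–10: has there been any foot reaction since the previous session and, if so, when did it start, how intense was it and how long did it last? The blinded assessor should ask it in the same words in both arms. Cover session 10 with a take-home card or one brief telephone or message contact about 72 hours afterwards. Extend the description of data collection in section 8 to include that last contact.

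The cost per participant is one question at each of nine visits that already take place, plus one card or short contact. The downsides are a minor burden and slightly higher reported reaction rates. Randomization and the primary analysis are unaffected.
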